## **6.9      Rescue medication**

Subjects will be allowed to use 100% oxygen as rescue medication during the study as described in [Section 7.1](#). If subjects require use of other rescue medication, they must contact the site immediately to be discontinued from the study. Every effort must be made to obtain study data for at least 24 hours after study medication has been administered. Use of rescue medication must be recorded on the Concomitant medications/Significant non-drug therapies CRF after start of study drug.

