# **7        Discontinuation and study completion**

## **7.1      Discontinuation of study treatment**

Subjects will be discontinued from the study if the subject receives additional treatment for the CH pain other than 100% oxygen after subject has had no relief of pain for at least 30 minutes following study medication administration. However data collected up to this point will be included in the assessment.

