**Table 4-1 Protocol deviation codes and analysis sets**

Category Deviation code	Text description of deviation	Data exclusion
Subjects are excluded from all (safety) analysis in case of these PDs:		
12	Written ICF not obtained	Exclude subject completely from all (safety) analysis sets
Subjects are excluded from PK analysis in case of these PDs:		Exclude subject from PK analysis set

*TRTD01      Study drug dosing error or incorrect treatment administered.*

---

Subjects are excluded from PD analysis in case of these PDs:		Exclude subject from PD analysis set
COMD01	Used prohibited treatment within 24 hours before receipt of study drug and within the first 30 minutes post dose.	
TRTD01	Study drug dosing error or incorrect treatment administered. Predose severity of CH is not at least moderate at one of the periods (unless there was a diary entry error)	Corporate Confidential Information

If updates to this table are needed, an amendment to the SAP needs to be implemented prior to DBL

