#### **6.1.2 Descriptive analyses**

If the second cohort (0.9 mg dose) is assessed then cohort will serve as a grouping factor for all relevant data listings.

The headache response will be defined at each post-dose timepoint separately and will be summarized by cohort, treatment and visit/timepoint using frequency tables. Percentage of subjects having received 100% oxygen therapy or sumatriptan at each time point will be tabulated by cohort and treatment.

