#### **6.1.3 Statistical model, assumptions and hypotheses**

A logistic regression analysis on the 30 minutes post-dosing data only with baseline headache severity (very severe, severe or moderate), CH type (episodic or chronic) and dose (0 for placebo, 1.5 mg or 0.9 mg for SOM230) as fixed effects will be used to assess the effect of SOM230 on headache response. Dose will be included as a categorical variable in the model. Placebo adjusted headache response rate will be provided. Headache response measurements after 100% oxygen therapy or sumatriptan will be set to missing, which will be considered as missing at random. The frequency and percentage of subjects with each response shall be displayed, along with the mean estimates, 90% confidence interval and p-value from the logistic regression analysis.

The following approaches will be taken if the 0.9 mg dose is assessed in the second cohort:

Placebo adjusted headache response rate will be obtained for each of the two SOM230 doses. A linear dose-response trend test will be constructed within the logistic regression framework using a contrast with the first order orthogonal polynomial coefficients. Pairwise comparisons and further dose-response assessments will be performed as appropriate. If there is no difference between the two SOM230 doses then a comparison between the pooled SOM230 treatment and placebo will be conducted.

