#### **6.1.4 Supportive analyses**

The McNemar test with or without stratification by CH type may also be used to compare headache response rates between treatments at 30 minutes post-dosing only.

If there are sufficient data to analyze, a Cox proportional hazard model with dose and CH type as classification factors and headache severity as a time dependent covariate will be used to analyze time to 100% oxygen therapy or sumatriptan. A random subject effect will be included in the model as well to account for the correlation among measurements from the same subject. This model will only be performed if the primary analysis indicates a significant result and there is sufficient data.

Joint modelling of the headache response and time to 100% oxygen therapy or sumatriptan data may be attempted as appropriate. This analysis will only be performed if a good response rate at 30 minutes versus placebo is detected.

Finally to avoid reducing statistical efficiency due to analyzing the dichotomized data, the headache severity measurements over time may be analyzed using a proportional-odds model similar to the aforementioned logistic regression model.

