#### **6.2.1.3 Statistical model, assumptions and hypotheses**

Pain free data will be analyzed using the same approach described for the primary variable. Pain free response measurements after 100% oxygen therapy or sumatriptan will be set to missing, which will be considered as missing at random.

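### For readings after 30 minutes, the SAP's set-to-missing rule and main rescue summaries cover only oxygen and sumatriptan, so relief after another rescue drug can count as SOM230 response

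*SAP*

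**What the plan says.** **SAP rule for readings after rescue.** For the primary model (6.1.3, 30-minute reading only): "Headache response measurements after 100% oxygen therapy or sumatriptan will be set to missing", with the gaps assumed to be missing at random. The all-timepoint sensitivity model (6.1.3.1) has the same wording. For the secondary endpoint (6.2.1.3): "Pain free response measurements after 100% oxygen therapy or sumatriptan will be set to missing".

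**SAP rescue summaries.** In 6.1.2: "Percentage of subjects having received 100% oxygen therapy or sumatriptan at each time point will be tabulated by cohort and treatment". In 6.1.4, a Cox model with "headache severity as a time dependent covariate will be used to analyze time to 100% oxygen therapy or sumatriptan". Separately, 6.2.1.2 reports the number and percentage of subjects given rescue medication at or after 30 minutes without naming a type, and 7.1.2 lists rescue medications.

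**SAP analysis set.** Section 4 limits the efficacy/PD set to subjects dosed in both periods without deviations that matter for efficacy. Table 4-1 excludes a subject under COMD01 for: "Used prohibited treatment within 24 hours before receipt of study drug and within the first 30 minutes post dose".

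**Protocol.** Under 6.9, a subject who needs a rescue drug other than oxygen is to contact the site and be discontinued, yet "Every effort must be made to obtain study data for at least 24 hours after study medication has been administered". Under 7.1, a subject who takes such treatment is discontinued, and "However data collected up to this point will be included in the assessment". Under 6.10, rescue oxygen may start 30 minutes after dosing and no other drug for cluster headache is allowed.

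**The concern.** The SAP extends the protocol's oxygen rule to one drug, sumatriptan, and stops there. The protocol itself foresees subjects who take something else and asks for their data afterwards. No visible SAP rule says what happens to those readings.

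Relief produced by the other drug would then count as study-drug response at later time points. The same attack would not be an event in the time-to-rescue model and would not appear in the rescue table by time point. These are attacks in which study treatment failed. If they sit mostly in the SOM230 period, the over-time response and the rescue comparison in 6.1.2 and 6.1.4 are tilted towards SOM230.

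**Working it through.** The documents state no figure on this point, so the check is first textual. The sizes that follow rest on stated assumptions.

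**1. Can such readings exist?** Yes. Protocol 6.9 seeks data for at least 24 hours after dosing, and Table 8-1 footnote 2 aims to discontinue only after 24 hours. Protocol 7.1 includes data up to the other treatment, which implies that later data are left out. The SAP turns this into no rule.

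**2. Which analyses are reached?**
- *30-minute models (6.1.3; pain-free endpoint in 6.2.1.3):* largely not. Permitted rescue starts only at 30 minutes, and earlier use of another drug is addressed by COMD01 and by the general exclusion in SAP 4.
- *Later readings:* the all-timepoint model (6.1.3.1), the time-to-response curves (6.1.3.3) and the Cox model (6.1.4), all run only after a significant primary result; the optional proportional-odds model; and the over-time tables (6.1.2, 6.2.1.2), which have no such condition.

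**3. In which attack?** A subject who uses another drug after placebo is to be discontinued. If discontinued before Period 2, that subject is not in the both-periods set. A subject who does so after SOM230 has had both doses and stays in.

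**4. Size for a later response rate.** Inputs: n=23 evaluable, and response rates of 30% (placebo) and 72% (SOM230), all from Protocol 11.6. Suppose all 23 have a reading and r of the other 22 respond.
- As written: (r+1)/23.
- Affected subject counted as a failure: r/23. Difference 1/23 = 4.3 points per subject. Three subjects give 3/23 = 13.0 points. With 30 subjects, 1/30 = 3.3 points each.
- Affected reading set to missing, as proposed below: r/22. The crude rate changes by (r+1)/23 − r/22 = (22−r)/506. With r=7 (about 30% of 22) this is 15/506 = 3.0 points; with r=16 (about 72%) it is 6/506 = 1.2 points.

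**5. Size for the rescue table.** Assumptions: every failure takes rescue; attacks are independent; a share q of failures uses a drug other than oxygen or sumatriptan; all such Period 1 users are lost; the table uses the efficacy set. For an inert drug (70% failures in both attacks), the rate of named rescue is 0.70(1−q)/(1−0.70q) on placebo and 0.70(1−q) on SOM230.

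| q | Placebo | SOM230 | Any rescue, all dosed attacks |
|---|---|---|---|
| 10% | 0.63/0.93 = 68% | 63% | 70% vs 70% |
| 20% | 0.56/0.86 = 65% | 56% | 70% vs 70% |
| 30% | 0.49/0.79 = 62% | 49% | 70% vs 70% |

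At the planned 72% response, the uncounted share of SOM230 attacks is 0.28q = 2.8%, 5.6% and 8.4%.

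**6. An effect in the other direction.** Under the same assumptions, losing Period 1 other-drug users removes placebo failures. Placebo response in the efficacy set becomes 0.30/(1−0.70q) = 32%, 35% and 38%, against 30%. This works against SOM230, and it reaches the 30-minute endpoint.

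**The case against.** The strongest reply is that little of importance is touched. The success criteria are set at 30 minutes, before permitted rescue has acted. COMD01 reads naturally as one window running from 24 hours before dosing to 30 minutes after it. The study is non-confirmatory, and the affected models are conditional or optional. This stands, and it confines the point to later readings and rescue summaries. The protection at 30 minutes does depend on that reading of 'and', and on 'prohibited treatment' covering the ban in Protocol 6.10 as well as the list in 5.2.

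Second, retention is inferred from silence, and Protocol 7.1 points the other way. That is fair. But a programmer who follows a closed list of two treatments would keep the readings, and the SAP is where Protocol 7.1 has to become a rule.

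Third, the rate of other-rescue use is unknown. Protocol 3.2 expects mainly non-sumatriptan users, but Protocol 1.1 names oxygen and sumatriptan as the only approved options, so oxygen may be the usual choice. This also stands: the q values are illustrations.

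Fourth, a Period 1 user of another drug might not always be lost. With 2 to 6 attacks a day and discontinuation aimed for after 24 hours, the second attack could be treated first. Hence the gap falls mainly, not only, on the SOM230 attack.

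A reader might infer that the primary result is biased towards SOM230, or that the SAP never counts other rescue. The documents support neither. The 30-minute models are largely protected, the loss of placebo failures works the other way, and SAP 6.2.1.2 and 7.1.2 report rescue medication without naming a type. SAP 1.4 does describe rescue as oxygen or sumatriptan only, so the count in 6.2.1.2 might be programmed that narrowly, but its wording does not say so.

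**Conclusion.** The concern holds for readings after 30 minutes and for the rescue summaries in SAP 6.1.2 and 6.1.4. Followed as written, the SAP keeps relief after another rescue drug as study-drug response and does not treat that attack as rescued in those two places, mainly in the SOM230 period. This departs from what Protocol 7.1 implies.

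Each relieved subject adds about 4.3 points to a later SOM230 response rate if all 23 have a reading and the alternative is to count a failure. Against setting the reading to missing, the crude change is about 1 to 3 points. The number of such subjects cannot be known from the documents. The models reached run only after a significant primary result or are optional, but that is when they would be used to support further development, and the over-time tables are produced regardless. It is a modest gap that is cheap to close before database lock.

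**What to change.** - **6.1.3, 6.1.3.1 and 6.2.1.3:** set to missing all readings after any treatment taken for the attack, consistent with Protocol 7.1. State that the over-time tables follow the same rule.
- **6.1.2 and 6.1.4:** define the rescue event as first use of any treatment for the attack. Tabulate rescue over all dosed attacks as well as in the efficacy set, so that Period 1 users who were then discontinued are seen.
- **COMD01:** write 'or' for 'and', so that use in either window excludes the subject.

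The cost is SAP wording and one derived flag. Rescue use and its timing are already recorded in the diary and on the concomitant-medication form. There will be slightly fewer later readings and possibly a less favourable late SOM230 response. If COMD01 is now applied as needing use in both windows, 'or' will exclude more subjects; if it is already read as one window, nothing changes.

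The protocol allows only oxygen as rescue, while SAP 1.4 also allows sumatriptan. Those passages must be reconciled separately; the analysis rule above does not depend on the outcome.

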### 3.2 Rationale for study design

Based on the nature of the studied disease and PK characteristics of SOM230, a single s.c. dose will provide an assessment of effect of SOM230 in managing cluster headache attack as well as the time to next attack. It is expected that a single dose of SOM230 will relieve the cluster headache attack and will delay the time to next attack resulting in reduced number of attacks per day. Given the nature of the disease (repeated attacks up to 8 attacks/day for up to 2 months), the relatively long half-life of SOM230, and to ensure consistency between attacks, treating 2 consecutive attacks in a one-sequence two-period design with a placebo treatment in Period 1 will be appropriate to cluster headache patients and will increase the statistical power by taking advantage of a within-patient comparison in the absence of carryover effects. The treatment effect will be confounded with the period effect in this one-sequence 2 period study. However, this is not a major concern considering the 2 periods are  $\leq 3$  days apart and we are looking for a substantial treatment effect. Subjects will be blinded to the sequence of treatment to minimize any potential bias. The Investigator input in this study will not have any influence on study outcome being solely entered by the subjects in the e-diary, thus the Investigators don't need to be blinded. Considering the severe pain associated with CH, patients benefiting from sumatriptan are expected to continue their conventional management that successfully relieves their pain. Accordingly, enrolled population in the study is expected to be mainly composed of non-sumatriptan users. To avoid confounding AE evaluation in

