# **11 Data analysis**

If the 0.9 mg dose is assessed then cohort will serve as a grouping factor for all relevant data listings. Additionally the effects of cohort on different endpoints will be explored and cohort may be included as a covariate in the corresponding analysis models as needed. A separate analysis may be performed for each cohort.

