### **11.4.2 Statistical model, hypothesis, and method of analysis**

A logistic regression analysis with baseline headache severity, CH type, dose, and dose by time interaction as fixed effects and subject as a random effect will be used to assess the effect of SOM230 on headache response over time. Dose and time will be included as categorical variables in the model. Placebo adjusted headache response rate at each time point will be provided. Headache response measurements after 100% oxygen therapy will be set to missing, which will be considered as missing at random.

The following approaches will be taken if the 0.9 mg dose is assessed in the second cohort:

Placebo adjusted headache response rate at each time point will be obtained for each of the two SOM230 doses. A linear dose-response trend test will be constructed within the logistic regression framework using a contrast with the first order orthogonal polynomial coefficients. Pairwise comparisons and further dose-response assessments will be performed as appropriate. If there is no difference between the two SOM230 doses then a comparison between the pooled SOM230 treatment and placebo will be conducted.

A subgroup analysis for non-sumatriptan users may be conducted as needed.

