#### **6.1.3.1 Sensitivity analyses**

Subjects are able to take a rescue medication at least 30 minutes following study medication administration. As a sensitivity analysis, the logistic regression analysis shall be repeated on all timepoints, where only the timepoints with at least 50% of non-missing data will be kept.

The logistic regression analysis with baseline headache severity (very severe, severe or moderate), CH type (episodic or chronic), dose (0 for placebo, 1.5 mg or 0.9 mg for SOM230), time and dose by time interaction as fixed effects and subject as a random effect will be used to assess the effect of SOM230 on headache response. Dose and time will be included as categorical variables in the model. Placebo adjusted headache response rate at each time point will be provided. Headache response measurements after 100% oxygen therapy or sumatriptan will be set to missing, which will be considered as missing at random. The frequency and percentage of subjects with each response shall be displayed, along with the mean estimates, 90% confidence interval and p-value from the logistic regression analysis.

The sensitivity logistic regression will only be performed if the primary analysis indicates a significant result.

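### SAP 6.1.3 ignores within-patient pairing and, if Cohort 2 runs, compares both doses with one placebo level pooled over two non-randomised cohorts

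*SAP*

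**What the plan says.** SAP 6.1.3 restricts the primary logistic regression to the 30-minute data. Its terms are baseline severity, CH type and "dose (0 for placebo, 1.5 mg or 0.9 mg for SOM230) as fixed effects". It names no subject effect and no cohort term. If Cohort 2 is run, "Placebo adjusted headache response rate will be obtained for each of the two SOM230 doses", and the trend test, the pairwise comparisons and the decision to pool the doses come from the same model.

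The protocol differs on both points:

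- **Subject.** The model in Protocol 11.4.2 has "dose by time interaction as fixed effects and subject as a random effect". Protocol 3.2 justifies the design by "taking advantage of a within-patient comparison in the absence of carryover effects".
- **Cohort.** Protocol 11 says that "the effects of cohort on different endpoints will be explored and cohort may be included as a covariate", and it also permits a separate analysis for each cohort. The synopsis says much the same. No criterion is given for using either option.

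The sensitivity model in SAP 6.1.3.1 restores the random subject effect. Its other terms include "dose (0 for placebo, 1.5 mg or 0.9 mg for SOM230), time and dose by time interaction as fixed effects", again without cohort. It is also conditional: "The sensitivity logistic regression will only be performed if the primary analysis indicates a significant result".

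Elsewhere in the visible SAP, cohort serves only to group listings and summaries.

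**The concern.** **Pairing.** Every patient in the SAP's efficacy set was dosed in both periods (SAP 4), so the placebo comparison is paired by design. A model without a subject effect treats the two attacks as coming from different people. SAP 6.1.3.2 still describes borrowing information from a patient's other values, which a single-timepoint model with no subject effect cannot do.

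**Shared placebo.** The cohorts are sequential, not randomised (Protocol 6.4) and have no patients in common (Protocol 4). The placebo procedure also differs: two injections in Cohort 1 and one in Cohort 2 (Protocol Table 8-1, footnote 7). With a single placebo level, each dose is judged partly against other patients' placebo attacks. A cohort difference that severity and CH type do not explain can then look like a dose difference. Protocol 3.2 gives learning about dose response as a reason for having two doses, so the 1.5 versus 0.9 mg contrast is where most is at stake.

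**Working it through.** **Inputs.** Protocol 11.6 gives response rates of 30% on placebo and 72% on either dose, correlation 0.25 and 23 evaluable patients per cohort. SAP 6.1.3 gives 90% intervals, so the nominal two-sided level is 10%. The cohort gap g is an assumption; the values 0, 6, 10 and 20 percentage points are illustrative. Severity and CH type are left out because their distributions are not given, so g is the gap remaining after them.

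**The plan's own figure.** Protocol 11.6 states about 80% power with 23 patients. An exact paired calculation of an estimated difference of at least 30 points gives 88.2%. A continuity-corrected normal approximation gives 80.2%. The estimator used is not stated, so the figure is not disputed, and the point does not depend on it.

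**Step 1: variances.** Placebo 0.30 × 0.70 = 0.21. Drug 0.72 × 0.28 = 0.2016. Covariance 0.25 × √(0.21 × 0.2016) = 0.0514.

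**Step 2: cost of ignoring pairing, within one cohort.**
- Independent: √((0.21 + 0.2016)/23) = 0.134.
- Paired: √((0.21 + 0.2016 − 2 × 0.0514)/23) = 0.116.
- The ratio is 1.15. A nominal 90% interval then reaches 1.645 × 1.15 = 1.90 true standard errors each way, which is about 94% coverage.

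This needs no cohort gap and no second cohort.

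**Step 3: effect of a cohort gap.** With equal cohorts, the shared placebo level sits midway between the two cohorts' placebo rates. Take g = 10 (placebo 25% in Cohort 1, 35% in Cohort 2) and the same odds ratio of 6.0 at both doses, which is the ratio implied by 30% and 72%. The drug rates are then 66.7% and 76.4%.

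| | True effect | Against shared 30% |
|---|---|---|
| 1.5 mg | 66.7 − 25 = 41.7 | 36.7 |
| 0.9 mg | 76.4 − 35 = 41.4 | 46.4 |

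Each dose is off by 5 points (g/2), in opposite directions. The difference between the doses is −9.7 instead of +0.3, so it is off by 10 (g). Unequal cohorts would split the shift unevenly.

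**Step 4: how often a dose difference is falsely detected.** Logistic fits to 20,000 simulated trials per gap, with placebo at 30% ± g/2 and drug at 72% ± g/2, so no true dose difference:

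| Model | g = 0 | 6 | 10 | 20 |
|---|---|---|---|---|
| As in SAP 6.1.3 | 9% | 12% | 18% | 42% |
| Cohort term, pairing ignored | 6% | 6% | 6% | 5% |
| Cohort term, subject-clustered SE | 10% | 10% | 9% | 9% |

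A repeat of the first row gave 43% at g = 20. Holding the odds ratio at 6.0 instead gave 9.4%, 17.7% and 41.9% at g = 0, 10 and 20. Both parts of the change are needed to bring the error rate to nominal.

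**Step 5: each dose against placebo.** Approximate coverage of the 90% interval from 6.1.3 is 93%, 92%, 90% and 78–81% at g = 0, 6, 10 and 20. The overstated standard error (0.115 in the model against a true 0.105 with shared placebo) masks the bias up to about g = 10.

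**Step 6: trend test.** The doses 0, 0.9 and 1.5 have mean 0.8, so dose-spaced coefficients are −0.8, 0.1 and 0.7. Shifts of g/2 in opposite directions move this contrast by (0.7 − 0.1) × g/2 = 0.3g. With no drug effect, it rejects in 6.5%, 7%, 8% and 13% of simulated trials at g = 0, 6, 10 and 20. With equally spaced coefficients the figures are 6.5%, 8%, 9.5% and 18%.

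**The case against.** **The shared placebo is a defensible trade.** The study is non-confirmatory and no document suggests a gap of any size. When the cohorts are alike, pooling placebo is more precise: 0.105 against 0.116 per dose. Comparing mean squared errors, own-cohort placebo does better only when g exceeds 2 × √(0.116² − 0.105²), which is about 9.7 points before rounding. This stands as a statement about precision. It does not answer the inflated error rate for the dose contrast, and it does not touch the pairing point.

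**The protocol already provides for it.** A cohort covariate and separate analyses are allowed, SAP 6.1.2 tabulates response by cohort and treatment, McNemar's test may be used (SAP 6.1.4), and chronic CH is capped at half of each cohort (Protocol 6.2). This also stands in part. But the tables are descriptive, McNemar's test and the covariate are optional, and the cap limits only one source of imbalance.

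**Stronger readings that the documents do not support:**
- A reader might infer that the trend test is badly distorted. It is mostly active against placebo and stays at or below nominal up to about g = 10.
- A reader might infer that the missing subject effect causes the bias. The missing cohort term causes it. Missing pairing only misstates the standard error, in the conservative direction for the placebo comparison. A random subject effect without a cohort term, as in 6.1.3.1, reduces the bias but does not remove it.
- A reader might infer that the protocol's exploration of cohort has been dropped. SAP 1.1 says the SAP implements the protocol, and part of the SAP is not visible. What can be said is that the visible text fixes no rule.
- A reader might infer that the Cohort 1 interim decision is biased by a cohort gap. No Cohort 2 data exist at that stage.

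**Conclusion.** The point holds, in two separate parts.

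1. **Pairing.** SAP 6.1.3 overstates the standard error of the placebo comparison by about 15% within a cohort, under the protocol's own planning values. This applies even if only Cohort 1 is analysed. It rests on the within-patient correlation being positive, as the protocol assumes.
2. **Cohort.** If Cohort 2 runs and a gap remains after severity and CH type, the 1.5 versus 0.9 mg contrast is biased by the full gap. False detection of a dose difference rises to about 12%, 18% and 42–43% at assumed gaps of 6, 10 and 20 points, against 10% nominal. Harm to each dose's own placebo comparison is modest unless the gap is large. With no gap there is no bias.

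Neither part concerns the period confounding that Protocol 3.2 acknowledges ("The treatment effect will be confounded with the period effect in this one-sequence 2 period study"), and the change below does not remove it. Nor does it remove a treatment effect that truly differs between cohorts. This should be settled before Cohort 2 data are seen; in a non-confirmatory study it does not undermine the trial.

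**What to change.** - In SAP 6.1.3, account for within-patient pairing, by subject-clustered standard errors or the protocol's subject effect. The error rates above were simulated with clustering only.
- When both cohorts are analysed, include cohort as a fixed effect in 6.1.3 and 6.1.3.1, so that each dose, and any pooled-dose comparison, is contrasted with its own cohort's placebo period.
- Describe 1.5 versus 0.9 mg as a non-randomised, between-cohort comparison.

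**Cost.** The pairing change has no real cost. The cohort term costs precision if the cohorts are truly alike. The standard error per dose rises about 10% (0.105 to 0.116). For the dose contrast it rises about 24%, from √(2 × 0.2016/23) = 0.132 to √2 × 0.116 = 0.164. Simulated power for each dose against placebo barely moves (98% to 97%). Power to see a real 20-point dose difference (72% against 52%) falls from about 41% to 30%.
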